PRO00040365: A comparison of the analgesic effects of pectointercostal fascial plane block (PIFB) alone versus PIFB with rectus sheath block (RSB) in cardiac surgery: a prospective, randomized controlled trial.

1. Protocol Title

A comparison of the analgesic effects of pectointercostal fascial plane block (PIFB) alone versus PIFB with rectus sheath block (RSB) in cardiac surgery: a prospective, randomized controlled trial.

NCT04908449

Updated 9.30.2024

PRO00040365: A comparison of the analgesic effects of pectointercostal fascial plane block (PIFB) alone versus PIFB with rectus sheath block (RSB) in cardiac surgery: a prospective, randomized controlled trial.

2. Purpose of the study

To determine if ultrasound-guided bilateral pectointercostal fascial plane blocks with bilateral rectus sheath blocks decrease pain scores, decrease opioid consumption, improve respiratory function, and improve quality of recovery in patients recovering from patients undergoing cardiac surgery in comparison to pectointercostal fascial plane blocks alone.

4. Design and Procedures

This is a single center, prospective, randomized, controlled, double-blinded study. We anticipate recruitment of 50-60 subjects (see #6 Recruitment and Compensation below), with 25-30 in each group. The definitive number will be determined by our final power analysis (see #12 Data analysis and statistical considerations below).

Primary Outcome:

Pain scores on a 0-10 numeric rating scale (NRS) at rest and with deep breathing at 1, 3, 6, 12, 18, and 24 hours post-extubation between subjects receiving PIFB + RSB versus subjects receiving only PIFB.

Secondary Outcomes:

- Total cumulative opioid consumption at 24 and 48 hours post-operatively.
- Change from baseline on incentive spirometry at 1, 3, 12, and 24 hours post-extubation
- Time from ICU arrival to liberation from mechanical ventilation
- ICU and hospital length of stay
- QoR-15 (Quality of Recovery) score²³ 24 hours after extubation

Preoperative Management

Subjects will be randomized on the morning of surgery to receive bilateral PIFB and bilateral RSB with local anesthetic versus bilateral PIFB with local anesthetic and bilateral RSB with saline (placebo).

Following the informed consent process, a member of the study team will instruct the patient on the appropriate use of incentive spirometry at the bedside and correct performance will be assessed. Three measurements will then be recorded to provide a baseline of incentive spirometry function.

Intraoperative Management

All subjects will receive the standard of care anesthetic regimen for their cardiac surgery, with specific medications at the discretion of their attending anesthesiologist, with the following exceptions:

- Fentanyl and sufentanil will be the only narcotics used intraoperatively.
- Fentanyl administration will be limited to bolus dosing, rather than infusions.
- Any sufentanil infusions must be stopped prior to or upon arrival in the intensive care unit.
- Sufentanil dosing range will be within 0.2-0.5 mcg/kg/hr. Extubation in the operating room is at the discretion of the attending anesthesiologist.
- Furthermore, neuromuscular blockade will be reversed prior to handoff in the ICU.

Postoperative Management

PRO00040365: A comparison of the analgesic effects of pectointercostal fascial plane block (PIFB) alone versus PIFB with rectus sheath block (RSB) in cardiac surgery: a prospective, randomized controlled trial.

Each PIFB will be performed with 15 mL of 0.25% bupivacaine with 5 mcg/ml of epinephrine, and bilateral RSB will be performed with an additional 20 mL of 0.25% bupivacaine with 5 mcg/ml of epinephrine (10mL on each side).

Single injection pectointercostal fascial plane blocks

The ultrasound-guided pectointercostal fascial plane blocks will be performed as follows:²⁰ a linear high frequency ultrasound probe will be placed in a parasagittal orientation between the third and fourth ribs, approximately one centimeter lateral to the sternal border, and all relevant structures will be identified, including the pectoralis major muscle, ribs, intercostal muscles, pleura, and any vasculature, including the internal mammary artery and vein. Color doppler will be used confirm the location of vasculature.

After skin cleaning with sterile chlorhexidine solution, a 9 cm 21 gauge insulated block needle (Sonoplex, Pajunk Medical Systems, Norcross, GA) will be inserted in an in-plane approach. In this way, both the needle shaft and tip can be visualized as the needle approaches the plane between the internal intercostal and pectoralis major muscles. The needle will be redirected as needed. Once satisfactory position of the needle tip is confirmed and after frequent negative aspiration, 20 mL of a solution containing 0.25% bupivacaine with epinephrine 5 mcg/ml will be slowly injected with intermittent aspiration. Spread of local anesthetic will be documented in the appropriate plane in real time. This procedure will be performed bilaterally.

All nerve blocks will be performed by an anesthesiologist experienced in regional anesthesia and/or a trainee supervised by an anesthesiologist experienced in regional anesthesia.

Single injection bilateral high rectus sheath nerve blocks

The ultrasound-guided rectus sheath blocks will be performed as described by Grant and Auyong²¹. A linear high frequency ultrasound probe will be placed in a transverse position in the midline, just inferior to the edge of the sternum. The probe will be moved laterally to visualize the lateral edge of the rectus abdominis muscle. The transversalis fascia, abdominal contents, and vasculature will be visualized, with color doppler confirmation of the location of vascular structures.

After skin cleaning with sterile chlorhexidine, a 9 cm 21G insulated block needle (Sonoplex, Pajunk Medical Systems, Norcross, GA) will be inserted from the lateral aspect of the ultrasound probe in a lateral to medial direction and aligned with the ultrasound scanning plane (in-plane approach). In this way, both the needle shaft and tip can be visualized as the needle approaches the rectus sheath plane, just deep to rectus abdominis and superficial to the posterior fascia. The needle will be redirected as needed. Once satisfactory position of the needle time is confirmed and after frequent negative aspiration, 10 mL of a solution containing 0.25% bupivacaine with epinephrine 5 mcg/ml or saline will be slowly injected with intermittent aspiration into this plane. Spread of local anesthetic will be documented in the appropriate plane in real time. This procedure will be repeated on the contralateral side.

Again, all nerve blocks will be performed by an anesthesiologist experienced in regional anesthesia and/or a trainee supervised by an anesthesiologist experienced in regional anesthesia.

Postoperative Evaluation

Evaluation of acute postoperative pain intensity using a 0-10 numeric rating scale (NRS) will be undertaken at the following time points, both at rest and with deep breathing:

PRO00040365: A comparison of the analgesic effects of pectointercostal fascial plane block (PIFB) alone versus PIFB with rectus sheath block (RSB) in cardiac surgery: a prospective, randomized controlled trial.

- 1, 3, 6, 12, 18, and 24 hours post-extubation

Incentive spirometry will be assessed at 1, 3, 12, and 24 hours post-extubation, with three measures taken at each time point in order to compare postoperative performance with baseline spirometry.

Review of the medical chart will be made post-operatively to gather other data, including total intraoperative oral morphine equivalent consumption, cumulative opioid consumption at 24 and 48 hours, time from ICU arrival to tracheal extubation, length of stay in the ICU, length of stay in the hospital, administration of other analgesic or sedating medications in the first 48 hours after extubation, and QoR-15 (Quality of Recovery) score²² administered 24 hours after extubation (with margin of error of 18-30 hours to avoid waking patients in the middle of the night). Occurrences of any adverse events reported by the subject or medical team will also be collected.

Collect additional surgical data: intraoperative OME, total surgical time, total cardiopulmonary bypass time, and total aortic crossclamp time. It is important to collect this data in order to control for these elements, as it is known that longer cardiopulmonary bypass time and aortic crossclamp time are associated with longer time to extubation and longer ICU length of stay²³.

5. Selection of subjects

Criteria for inclusion:

- Subjects scheduled for elective cardiac surgery involving primary median sternotomy and subxiphoid chest tube placement
- Age 18-85 years of age
- BMI 18-50 kg/m²
- Weight > 60 kg

Criteria for exclusion:

- Left ventricular ejection fraction (LVEF) < 30%
- Preoperative, intraoperative, or immediate post-operative placement of intra-aortic balloon pump or deployment of extra-corporeal membrane oxygenation (ECMO)
- Inability to understand or speak English
- Allergy to bupivacaine or other amide local anesthetic
- Contraindication to peripheral nerve block (e.g. local infection, previous trauma to the block site)
- Chronic opioid consumption (daily oral morphine equivalent of >20 mg) in the past three months
- Severe pulmonary or hepatic disease
- Neurological deficit or disorder
- Suspected or known addiction to or abuse of illicit drug(s), prescription medicine(s), or alcohol within the past two years
- Uncontrolled anxiety, schizophrenia, or other severe psychiatric disorder
- Patients who remain intubated for >24 hours after the stop of anesthesia will be removed from the study

6. Subject recruitment and compensation

Participating cardiac surgeons will share a basic study information sheet with potential subjects in their pre-operative surgery clinic visit. Potential subjects (see inclusion criteria above) will be identified on the surgical schedule by a member of the study team, typically at least one day in advance of the surgical procedure. These individuals will be contacted by telephone or in-person, if they are pre-admitted, and asked for permission to discuss the study. The purpose of the study will be explained, the consent form

PRO00040365: A comparison of the analgesic effects of pectointercostal fascial plane block (PIFB) alone versus PIFB with rectus sheath block (RSB) in cardiac surgery: a prospective, randomized controlled trial.

read out loud, and any questions answered. Potential subjects will be encouraged to take time to discuss the study with family and will be told that there will be additional time to answer any questions on the day of surgery (or date prior, if pre-admitted). Potential subjects will be told that there is no obligation to take part in the study and their decision will not affect the quality of their care.

On the day of surgery or day prior to surgery (if pre-admitted), one of the investigators will approach the potential subject in his/her hospital room or the preoperative area, as appropriate, and answer any remaining questions. Subjects that indicate their interest in participating will then sign an informed consent and complete a HIPAA authorization form. There will be no compensation for subjects for their participation.

7. Consent process

The consent process will be conducted by one of the study team members. The consent process will take place in the patient's hospital room or the pre-operative area, depending on whether or not the patient has been pre-admitted. Throughout the consent process, measures will be taken to maintain privacy, such as conducting face-to-face conversations in private rooms. As much time as necessary will be spent with each potential subject to sufficiently explain and answer all questions and address all concerns they may have in regard to the study and/or consent process.

8. Subject's Capacity to Give Legally Effective Consent

Subjects who do not have the capacity to give legal consent will not be approached for participation in this study.

9. Study interventions

See #4.

10. Risk/benefit assessment

Risk to the subject

This study involves multiple injections, either with a local anesthetic solution or saline. Risks associated with the nerve block include bleeding, infection, nerve damage, and damage to surrounding structures, including blood vessels and lungs.

Benefits to the subject

The potential benefit of participating in the study is that patients receiving PIFB + RSB may require less pain medication resulting in fewer side effects, experience improved respiratory function, and achieve milestones sooner than those who do not receive PIFB + RSB blocks.

11. Costs

There will be no costs to the subject for participation in the study. Subjects will not be compensated for their participation.

12. Data analysis and statistical considerations

In order to appropriately complete our power analysis, following IRB approval and prior to patient recruitment we will review charts of 10-20 patients who have undergone CABG surgery and who have

PRO00040365: A comparison of the analgesic effects of pectointercostal fascial plane block (PIFB) alone versus PIFB with rectus sheath block (RSB) in cardiac surgery: a prospective, randomized controlled trial.

received PIFBs within the last year at our institution in order to define baseline pain scores within the first 24 hours and opioid usage within the first 48 hours postoperatively.

Our data analysis plan is as follows: since we had no pilot data on AUC pain outcomes, we considered a conservative scenario when the two outcomes are uncorrelated and described detectable differences between study outcomes in terms of standard deviations (SDs). To evaluate power properties of the Hotelling T2 at $\text{ALPHA} = 5\%$ test, we considered statistical power of two two-sample t-tests at $\text{ALPHA} = 2.5\%$. At 24 patients per group, the detectable at 80% power difference between group means = 0.9 SDs ($\text{ALPHA} = 2.5\%$). If the normality assumption is violated, Mann-Whitney test will have the same power properties at 25 patients per group. At 29 patients per group, the detectable at 80% power difference between group means = 0.8 SDs ($\text{ALPHA} = 2.5\%$); Mann-Whitney nonparametric alternative will have the same power properties at 30 patients per group.

13. Data & Safety Monitoring

In accordance with federal regulations the PI will monitor for, review, and promptly report to the IRB, appropriate institutional officials, sponsor, coordinating center and the appropriate regulatory agency head all unanticipated problems involving risks to subjects or others that occur in the course of a subject's participation in a research study, all AE reports will be reported per the MCW IRB policies. PI will be monitoring all AEs and submitting reports to the IRB per MCW IRB policy.

Furthermore, an independent monitor has been chosen for the study, and this individual is a regional anesthesiologist, who will not be involved in study proceedings but who will be updated on study progress as per the DSMP.

14. Privacy, Data Storage and Confidentiality

Potential subjects and their families will be approached in private rooms or preoperative bays. Any guests not involved in the consent process will be asked to leave the room during any communications, unless the subject allows them to be present. Efforts to maintain subject confidentiality will include assignment of following Federal Privacy Regulations which provide safeguards for privacy, security, and authorized access. Except when required by law, subjects will not be identified by name, social security number, address, telephone number, or any other direct personal identifier in study records disclosed outside of Medical College of Wisconsin or Froedtert Hospital. Subjects will be not be revealed in any reports or publications resulting from this study. For records disclosed outside of MCW/Froedtert, subjects will be assigned a unique code number. The paper/electronic data will be stored as per the data safety and monitoring plan.

The only exception to the above is that the Investigational Drug Services pharmacy may unblind in cases of medical emergency with written or verbal consent from [name] (PI). Only the investigator will be unblinded to the subject's treatment group, and this will be done only in the case of a medical emergency.

References

2. Lee, C. Y. *et al.* A Randomized Controlled Trial of Liposomal Bupivacaine Parasternal Intercostal Block for Sternotomy. *Ann Thorac Surg* **107**, 128-134, doi:10.1016/j.athoracsur.2018.06.081 (2019).

PRO00040365: A comparison of the analgesic effects of pectointercostal fascial plane block (PIFB) alone versus PIFB with rectus sheath block (RSB) in cardiac surgery: a prospective, randomized controlled trial.

3. Janssen-Sanders Ll, G. L., Bruins P, Driessen A, Morshuis W, Knibbe C, Dongen EV. Pain in intensive care after sternotomy is predictive for chronic thoracic pain. *Critical Care* **12**, P510, doi:10.1186/cc6731 (2008).
4. Dogan Baki, E. et al. Effects of Parasternal Block on Acute and Chronic Pain in Patients Undergoing Coronary Artery Surgery. *Semin Cardiothorac Vasc Anesth* **20**, 205-212, doi:10.1177/1089253215576756 (2016).

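### Section 4 gives the PIFB volume as 15 mL per side in one place and 20 mL per side in another, so neither arm has a single specified bupivacaine dose (control 75 or 100 mg, active 125 or 150 mg).

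*Combined protocol and SAP*

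**What the plan says.** The dosing paragraph of Section 4, under Postoperative Management, reads: "Each PIFB will be performed with 15 mL of 0.25% bupivacaine with 5 mcg/ml of epinephrine". It goes on to give the RSB a further 20 mL of the same solution in total, 10 mL per side.

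The next subsection, on the single-injection PIFB, describes how the same block is done. Once the needle tip is in place, "20 mL of a solution containing 0.25% bupivacaine with epinephrine 5 mcg/ml will be slowly injected with intermittent aspiration". The paragraph ends: "This procedure will be performed bilaterally".

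The RSB subsection gives "10 mL of a solution containing 0.25% bupivacaine with epinephrine 5 mcg/ml or saline will be slowly injected", repeated on the other side, which agrees with the dosing paragraph. Under Preoperative Management in Section 4, control patients receive the PIFB with local anesthetic and the RSB with saline. The control arm's only local anesthetic from the study blocks is therefore the PIFB.

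**The concern.** Drug, concentration, epinephrine content and block are the same in the two paragraphs. Only the volume differs, and an operator cannot follow both. These are also the two places staff would look: the statement of dose and the operator's instructions. Blocks may be done by different anesthesiologists or supervised trainees, so two operators could each follow the protocol and give different doses. Neither dose could be recorded as a deviation.

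Three things are at stake.

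- **Exposure.** Total local anesthetic and epinephrine cannot be stated per arm for safety review, for reporting or for anyone repeating the trial.
- **Interpretation.** The trial asks what the RSB adds to a PIFB. The answer applies to the PIFB dose actually given, and the protocol names two.
- **Precision.** If practice were mixed, the background treatment would vary between patients. That could add noise to the pain scores in a trial of 25 to 30 per group.

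**Working it through.** **Could the two statements be compatible?** Three readings were tried.

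1. *20 mL as the total for both sides.* This does not fit. The volume is tied to one confirmed needle position, and the procedure is then done bilaterally. It would also mean 10 mL per side, which still conflicts with 15 mL.
2. *15 mL as the total for both sides.* This does not fit, because the sentence gives the volume for each PIFB.
3. *A text-extraction fault or superseded text.* This is unlikely. Both figures stand in running prose, and the document has no amendment log that would retire either one. The RSB volume agrees in both places (2 × 10 = 20 mL), so the conflict is confined to the PIFB.

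**Inputs.** All are from Section 4 unless noted: PIFB volume v = 15 or 20 mL per side; RSB 10 mL per side; bupivacaine 0.25% = 2.5 mg/mL; epinephrine 5 mcg/mL; saline RSB in the control arm; weight above 60 kg (Section 5).

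**Formulas.**

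- Control bupivacaine = 2 × v × 2.5
- Active bupivacaine = (2 × v + 2 × 10) × 2.5
- Epinephrine = the same volumes × 5 mcg

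The protocol states no total dose in milligrams, so there is no total of its own to reproduce.

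| | Dosing paragraph (15 mL) | Technique paragraph (20 mL) |
|---|---|---|
| Control, local anesthetic volume | 30 mL | 40 mL |
| Control, bupivacaine | 75 mg | 100 mg |
| Control, epinephrine | 150 mcg | 200 mcg |
| Active, local anesthetic volume | 50 mL | 60 mL |
| Active, bupivacaine | 125 mg | 150 mg |
| Active, epinephrine | 250 mcg | 300 mcg |
| Active minus control, bupivacaine | 50 mg | 50 mg |
| RSB dose as share of control dose | 50/75 = 67% | 50/100 = 50% |

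The PIFB dose differs by 100 − 75 = 25 mg, and 25/75 = 33%. That 25 mg is half of the 50 mg RSB dose under test.

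At the 60 kg weight limit the active-arm dose is 125/60 = 2.08 or 150/60 = 2.50 mg/kg. The control-arm dose is 75/60 = 1.25 or 100/60 = 1.67 mg/kg. These are limiting values for the lightest eligible patients.

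**The case against.** The contradiction itself is hard to contest. The case on the other side is about its consequences.

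- **The comparison is intact.** The randomized contrast is RSB with local anesthetic against RSB with saline, on a common PIFB. The difference is 50 mg under either volume. Allocation is randomized and the study is described as double-blinded, so nothing ties PIFB volume to arm. The 67% and 50% shares are the same 50 mg set against different bases. *This stands:* the inconsistency is common to both arms and is not a source of bias.
- **Mixed practice is not shown.** This is a single-center trial, and its staff may have used one volume throughout. The documents give no dose-response figure from which to work out an effect on the spread of pain scores. *This stands:* added variation is a risk, not a demonstrated effect.
- **The ambiguity is bounded.** The protocol gives two values, not none, and they are 25 mg apart. *This stands as a matter of wording.*
- **The mg/kg figures have no benchmark.** The documents state no maximum bupivacaine dose. *This stands:* the figures are context only, and no toxicity conclusion is drawn from them.
- **Pharmacy documents may already fix one volume.** Those documents are not available here, and the pharmacy appears in the protocol only in connection with emergency unblinding (Section 14). One settled volume in practice would lessen the effect but would not repair the protocol text.

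**Conclusion.** The concern holds. Section 4 states two incompatible volumes for an injection given to every participant, and no other text resolves them. The gap is 25 mg of bupivacaine and 50 mcg of epinephrine per patient in both arms, a 33% difference in the PIFB dose. In the control arm the PIFB is the only study block containing local anesthetic.

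The ground for requiring a correction is narrow but firm: the protocol does not fix the dose of a study intervention. It does not rest on bias in the primary comparison, on evidence of mixed dosing or on a safety threshold. The size follows from the stated volumes and concentrations, with the 20 mL read as a per-side volume, which is the only reading the technique paragraph supports. Nothing here indicates which volume is right.

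**What to change.** - Reconcile the dosing paragraph and the PIFB technique paragraph in Section 4 to a single volume per side. The choice belongs to the investigator and sponsor.
- State the resulting total bupivacaine and epinephrine for each arm, so that the two descriptions can be checked against each other.
- Check that the pharmacy preparation instructions match the reconciled volume.
- If patients have already been treated, record the PIFB volume each received and report it by arm.

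The cost is a one-line correction by amendment and a check of the pharmacy order set. If treatment has begun, it also includes retrieving the volumes given, to the extent they were recorded. Sample size and analysis are unaffected.

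### Adverse events are collected only when someone reports them, and section 10 names no systemic risk of the extra drug that separates the arms

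*Combined protocol and SAP*

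**What the plan says.** Section 4 (Postoperative Evaluation) contains the only rule for collecting adverse events, at the end of the chart-review paragraph: "Occurrences of any adverse events reported by the subject or medical team will also be collected". Adverse events are not among the primary or secondary outcomes in section 4, and section 12 plans no summary or comparison of them.

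The rectus sheath block is given in both arms, and the contents of the syringe depend on the arm: "10 mL of a solution containing 0.25% bupivacaine with epinephrine 5 mcg/ml or saline will be slowly injected", then repeated on the other side. Both arms also receive bilateral PIFB with bupivacaine and epinephrine.

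Section 10 introduces the risks with "This study involves multiple injections, either with a local anesthetic solution or saline" and continues: "Risks associated with the nerve block include bleeding, infection, nerve damage, and damage to surrounding structures, including blood vessels and lungs". No systemic effect of bupivacaine or epinephrine follows. Section 5 does exclude patients allergic to amide local anesthetics.

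Section 13 has the principal investigator monitor all adverse events and report them under IRB policy. An independent regional anesthesiologist is kept informed under a data and safety monitoring plan (DSMP), which is not among the supplied documents.

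**The concern.** The needle procedures are common to both arms, so they should not produce a difference in harm. The additional drug could, yet it has no named risk and no planned measurement.

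Spontaneous reporting usually finds fewer events than a fixed list checked for everyone. Here the weakest period is likely to be just after injection. The blocks are described under Postoperative Management, and the earliest scheduled postoperative assessment is 1 hour after extubation. Some patients will still be ventilated on reaching the ICU, since time from ICU arrival to liberation from ventilation is itself an outcome. Those patients cannot speak for themselves until extubated, and the clinical team has no list of events that the study wants flagged.

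Reporting could also be uneven. If the added block shortens ventilation, which the trial sets out to examine, patients in that arm can describe symptoms earlier. At stake is whether the trial report, and the counts reaching the independent monitor, can support any statement about harm from the added block. The primary pain analysis is not affected.

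**Working it through.** The protocol states no adverse event rate and no safety precision, so there is no figure of its own to reproduce. The check compares the text section by section and then adds some simple arithmetic.

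**1. What separates the arms** (volumes and concentrations from section 4; 0.25% = 2.5 mg/mL)
- Rectus sheath block, active arm: 2 × 10 mL = 20 mL. Bupivacaine 20 × 2.5 = 50 mg; epinephrine 20 × 5 = 100 mcg. Control arm: saline.
- PIFB, both arms. One sentence in section 4 reads "Each PIFB will be performed with 15 mL of 0.25% bupivacaine with 5 mcg/ml of epinephrine", while the PIFB procedure text gives 20 mL per side. These conflict and must be reconciled.

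| PIFB volume per side | Control: bupivacaine / epinephrine | Active: bupivacaine / epinephrine |
|---|---|---|
| 15 mL | 2 × 15 × 2.5 = 75 mg / 150 mcg | 75 + 50 = 125 mg / 250 mcg |
| 20 mL | 2 × 20 × 2.5 = 100 mg / 200 mcg | 100 + 50 = 150 mg / 300 mcg |

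The difference between arms is 50 mg and 100 mcg under either reading.

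**2. When patients are assessed**
- Pain scores and spirometry start 1 hour after extubation; QoR-15 is at 24 hours (allowed 18 to 30).
- Section 5 removes patients intubated for more than 24 hours after anesthesia stops. A retained patient could therefore go up to 24 + 1 = 25 hours after anesthesia before the first scheduled postoperative assessment. The interval from the block cannot be stated, because no block time is listed among the data collected.
- No section says whether adverse events in patients removed under that rule are kept.

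**3. What incomplete capture does**
- If a fraction c of events is recorded equally in both arms, the expected observed risk difference is c × (p1 − p0), smaller than the true one. If capture differs by arm, it is c1 × p1 − c0 × p0, which can err in either direction. The documents give no value for c, so none is used.

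**4. What the sample size allows even with full capture** (25 to 30 per group, section 4)
- Zero events in an arm, one-sided 95% upper limit = 1 − 0.05^(1/n): n = 25 gives 11.3%; n = 30 gives 9.5%.
- Chance of at least one event = 1 − (1 − p)^n, with p assumed: 22% to 26% at p = 1%; 72% to 79% at p = 5%.
- Power to detect 5% against 20% (assumed rates; two-sided alpha 0.05, normal approximation): 36% to 42%.

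Steps 1 to 3 are the finding. Step 4 describes the size of the trial, which the fix does not change; it shows why the table by arm should be descriptive.

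**The case against.** The strongest reply is that safety oversight exists. Section 13 has the principal investigator monitor all adverse events and names an independent monitor, and the DSMP or the consent form may hold the event list and the drug risks. This stands as a limit: the point covers the supplied text only, and a reader should not infer that harms go unmonitored. But oversight acts on events already recorded, and nothing in section 13 adds solicited events, assessment times or a comparison by arm.

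Several stronger readings are tempting, and the documents do not support them:
- **That the contrast is drug against no drug.** Control patients receive the same drugs through the PIFB; the contrast is an additional amount.
- **That events in sedated patients cannot be reported.** The medical team is a named reporting route, and section 4 allows extubation in the operating room. How many patients are sedated at injection is not stated.
- **That section 10 omits abdominal puncture.** Its reference to surrounding structures is not exhaustive and can cover it. Puncture is also a needle risk common to both arms.
- **That opioid side effects go uncollected.** Section 10 offers that "patients receiving PIFB + RSB may require less pain medication resulting in fewer side effects", and no such effect is a named outcome. But QoR-15 is collected and its items are not reproduced, so the claim cannot be verified.

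It is also fair that the trial has no safety objective and is too small to settle one, and that blinding limits uneven reporting by staff.

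**Conclusion.** The point holds for the supplied protocol text. Collection is passive, no stated window covers block to extubation, no tabulation by arm is planned, and section 10 names no systemic risk of the additional 50 mg of bupivacaine and 100 mcg of epinephrine. A comparison of harms by arm would rest on incomplete and possibly uneven reporting.

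A reader might want a number for the under-count. None can be given, because the documents supply neither an event rate nor a capture rate. The 11.3% and 9.5% limits assume full capture and so do not measure this defect.

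The conclusion assumes that the DSMP and consent form do not already specify systematic capture and the drug risks; if they do, the protocol need only be aligned with them. The change is worth making because it is cheap and replaces a stated passive method with a better one. It is not a flaw in the efficacy comparison.

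**What to change.** - Add the time of the block to the data collected.
- In the chart review already planned, have staff blinded to arm extract a short fixed list of events for every patient, whether or not anyone reported them. For example: new arrhythmia, seizure, hypotension needing new treatment, pneumothorax, block-site haematoma, and antiemetic use to 24 hours. Define each event and state the window, starting at the block. The protocol calls the trial double-blinded but does not say that the chart review is, so this should be written in.
- Keep patients later removed for prolonged intubation in this extraction.
- Tabulate the events by arm, descriptively, and send the counts to the independent monitor.
- Add systemic local-anesthetic and epinephrine effects to the section 10 risk list. Check the DSMP and consent form for consistency, and reconcile the two PIFB volumes so that total exposure is clear.

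The cost is a few chart fields and one table, with no extra visit or staff. The drawback is that more events routine after cardiac surgery will be listed in both arms, and 25 to 30 patients per arm will still not exclude uncommon harm.
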